5.4.2 Secondary Efficacy Analyses

Key Secondary Endpoint Analysis

If the primary endpoint is statistically significant, then key secondary endpoints will be tested in the following order: change from baseline in ADCOMS at 24 month in the combined studies, and change from baseline in amyloid PET SUVR at 24 months for brain amyloid levels in the combined studies. Each test will be performed at a significance level of alpha 0.05 (2-sided) and will only be performed if the preceding test is statistically significant. The MMRM described for primary efficacy analysis will be used on the FAS to test the key secondary endpoints, using baseline value corresponding to the response variable in the model. For ADCOMS, The MMRM

analysis will be conducted on FAS, by censoring the data after intercurrent events as sensitivity analyses.

The amyloid PET SUVR from three tracers (Florbetapir, Florbetaben, and Flutemetamol) will be standardized using the centiloid scale and combined for the key secondary endpoint. The following equations are used to get centiloid scale in mean composite SUVR for each tracer (Adamczuk, 2019).

- Florbetapir: mean composite SUVR in centiloid scale = $205.72 * \text{mean composite SUVR} - 209.63$
 - Mean composite SUVR is simple average of cingulate, frontal, parietal, and temporal rollups
 - Whole cerebellum region is used as reference region
- Florbetaben: mean composite SUVR in centiloid scale = $175.57 * \text{mean composite SUVR} - 173.21$
 - Mean composite SUVR is simple average of cingulate, frontal, parietal, and temporal rollups
 - Whole cerebellum region is used as reference region
- Flutemetamol: mean composite SUVR in centiloid scale = $145.58 * \text{mean composite SUVR} - 139.29$
 - Mean composite SUVR is simple average of cingulate, frontal, parietal, and temporal rollups
 - Whole cerebellum region is used as reference region

Other amyloid PET SUVR parameters (i.e., mean composite SUVR described above using whole cerebellum, cerebellar grey matter, or subcortical white matter as separate reference region for Florbetapir and Flutemetamol and mean composite SUVR, which is simple average of cingulate, frontal, parietal, temporal, and occipital rollups, using whole cerebellum, cerebellar grey matter, or subcortical white matter as separate reference region for Florbetaben) will be summarized by tracer as biomarker endpoints using the same statistical method.

Other Secondary Endpoint Analysis

Time to worsening of CDR scores by 24 months

Time to worsening of CDR scores by 24 months will be analyzed on the FAS using a Cox regression model for treatment effect, adjusting for randomization stratification factors. Median, 1st quartile, and 3rd quartile of time to worsening of CDR scores and proportion of subjects with

worsening of CDR scores at 6, 12, 18, and 24 months will be estimated using Kaplan-Meier method based on time to worsening of CDR scores. Time to worsening of CDR scores is defined as time from randomization to worsening of the CDR scores (ie, the second worsening - increase from baseline by at least 0.5 points on the global CDR score, in 2 consecutive visits [at least 8 weeks apart]). For example, if the global CDR scores are 0.5 at baseline, 1.0 at Visit 6 [3 months visit], 1.0 at Visit 7 [6 months visit], this subject have worsening of CDR scores at Visit 7 [6 months visit]. If the global CDR scores are 0.5 at baseline, 1.0 at Visit 6 [3 months visit], 0.5 at Visit 7 [6 months visit], the subject does NOT have worsening of CDR scores at Visit 7 [6 months visit]). If randomization date is not same as the first dose date, the first dose date will be used instead of randomization date. If last available assessment shows worsening of the global CDR score, it will be considered as a censor. For subjects whose CDR scores have not worsened by the end of study, the time to worsening of CDR scores will be censored at the date of last CDR assessment for these subjects. All post-baseline assessments within Study Day 753 (upper limit of 24 months analysis visit for CDR assessment) will be included.

The same analysis by censoring the data after intercurrent events (treatment discontinuation, and initiation/change of AD medications) will be conducted as sensitivity analysis.

Time to conversion to dementia by 24 months for subjects who were not clinically staged as dementia at Baseline based on clinical diagnosis

This endpoint will be analyzed on the FAS using a Cox regression model for treatment effect, adjusting for randomization stratification factors. Median, 1st quartile, 3rd quartile of time to conversion to dementia and proportion of subjects with dementia diagnosis at 6, 12, 18, and 24 months will be estimated using Kaplan-Meier method based on time to conversion to dementia in clinical diagnosis. Time to conversion to dementia for subjects who were not clinically staged as dementia at baseline is defined as time from randomization to conversion to dementia in clinical diagnosis. If randomization date is not same as the first dose date, the first dose date will be used instead of randomization date. For subjects without clinical dementia by the end of study, the time to conversion to dementia will be censored at the date of last dementia diagnosis for these subjects. All post-baseline assessments within Study Day 753 (upper limit of 24 months analysis visit for CDR assessment) will be included.

The same analysis by censoring the data after intercurrent events (treatment discontinuation, and initiation/change of AD medications) will be conducted as sensitivity analysis.

The diagnosis and clinical disease staging will be verified via a central review process and adjudicated if necessary (adjudication will only occur when there is a discrepancy between the diagnosis and clinical disease staging made by the site compared to that determined by the central review process; moreover, where adjudication is required, it will be undertaken by an independent assessor(s)).

The rate of change over time (mean slope) based on CDR-SB score over 24 months

The rate of change over time (mean slope) for the change from baseline in CDR-SB will be analyzed on the FAS using linear mixed effects (LME) models for multivariate normal data

derived from a random coefficient model (slope analysis), where the mean slope in each group depends on a continuous assessment time. The LME model will include assessment time, and treatment group-by-assessment time as well as random intercept and slope (unstructured). The Kenward-Roger approximation will be used to estimate the denominator degrees of freedom.

Other continuous endpoints

The other continuous secondary efficacy endpoints will be analyzed using the same MMRM model as the primary efficacy analysis to compare elenbecestat 50 mg versus placebo on the FAS, using baseline value corresponding to the response variable in the model. These endpoints include:

- Change from baseline in the CDR-SB at 24 months for subjects enriched by baseline PET SUVR, eg, between 1.2 and 1.6, in the combined studies
- Change from baseline in the ADCOMS at 24 months for subjects enriched by baseline PET SUVR, eg, between 1.2 and 1.6, in the combined studies
- Change from baseline in ADAS-cog₁₁, ADAS-cog₁₄, MMSE, and FAQ at 24 months in the combined studies
- Change from baseline in ADAS-cog₁₄ Word List (immediate recall and delayed recall) at 24 months in the combined studies

The following amyloid PET mean composite SUVR in centiloid scale ([Adamczuk, 2019](#)) will be used to enrich the population, extrapolated from the 1.2 to 1.6 SUVR calculated for Florbetapir ([Dhadda, 2018](#)) : 37.234 to 119.522 (equivalent to 1.198633 to 1.667324 in Florbetaben and 1.212557 to 1.777799 in Flutemetamol) (Adamczuk [2019])

With regard to the change from baseline in ADAS-cog₁₄ Word List, it includes the immediate and delayed recall tasks, their scores will be part of the ADAS-cog₁₄ assessment (Item 1 and 4).

For ADAS-cog₁₁, ADAS-cog₁₄, MMSE, FAQ, and ADAS-cog₁₄ Word List (immediate recall and delayed recall), the MMRM analysis will be conducted on FAS, by censoring the data after intercurrent events (treatment discontinuation, and initiation/change of AD medications) as sensitivity analyses.

The MMRM using the change from baseline at last on treatment visit and 12 week Follow-up visit will be conducted based on the subjects in FAS who have the assessments at both visits to evaluate the change after last dose in CDR-SB, ADCOMS, ADAS-cog₁₁, ADAS-cog₁₄, MMSE, and ADAS-cog₁₄ Word List (immediate recall and delayed recall) instead of the analysis for the change from baseline in CDR-SB at 27 months. The same MMRM as the primary efficacy analysis (except excluding baseline by visit interaction) will be used with appropriate contrast to evaluate the difference between last on treatment visit and 12 week Follow-up visit by each treatment group.

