5.3.2 Adjustments for Covariates of Interest

The primary, secondary, and exploratory efficacy endpoints will include the stratification variables (region, concurrent AD medication use, clinical disease staging), *ApoE4* status, and baseline value of the endpoint (if applicable) as covariates. For mixed-effects models for repeated measures (MMRM), the baseline-by-visit interaction will also be included. To follow ITT principle, the classification used at randomization will be used for the adjustments for covariates of interest.

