5.3.4 Examination of Subgroups

Subgroup analysis will be performed for the primary, secondary efficacy endpoints, and biomarker endpoints. The subgroups include:

- age (<65, 65 to <80, and ≥ 80 years)
- sex
- race
- ethnicity
- region ([section 5.3.1](#))
- concurrent AD medication use (yes, no) at baseline

- clinical disease staging (MCI due to AD, early stages of mild AD) at baseline
- *ApoE4* status
- baseline CDR Memory Box score
- very mild subjects (baseline CDR-SB \leq 1.5 and baseline MMSE \geq 27)
- baseline amyloid PET SUVR 1.2 to 1.6
- amyloid PET tracer (Florbetapir, Florbetaben, and Flutemetamol; only for amyloid PET SUVR)

For concurrent AD medication use, clinical disease staging, and region, the actual classification (not the IxRS classification) will be used.

As described in [Section 5](#) Statistical methods, the efficacy will also be evaluated within each study (E2609-G000-301 and E2609-G000-302).

Forest plot for primary and key secondary endpoint (only ADCOMS) will be generated to visually display the treatment difference with 95% confidence interval, no significance tests will be performed in the subgroups.

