5.4 EFFICACY ANALYSES

5.4.1 Primary Efficacy Analysis

Regarding the primary endpoint, the null hypothesis is that there is no difference in the mean change from baseline in CDR-SB at 24 months between elenbecestat 50 mg per day and placebo; the corresponding alternative hypothesis is that there is a difference in the mean change from baseline in CDR-SB at 24 months between elenbecestat 50 mg per day and placebo.

The primary analysis will be based on the ITT philosophy without regard to adherence to treatment. All observed data will be included in the primary analysis, regardless of treatment discontinuation or change in concomitant AD medications. The primary analysis of the change from baseline in CDR-SB at 24 months will be performed to compare elenbecestat 50 mg per day versus placebo using a MMRM on the FAS. The MMRM model will include baseline CDR-SB and baseline CDR-SB by visit interaction as a covariate, with treatment group, visit, randomization stratification variables (ie, region [7 levels], clinical disease staging [MCI due to AD, early stage of mild AD], and concurrent AD medication use at randomization (Visit 2) [yes, no]), *ApoE4* status, and treatment group-by-visit interaction as fixed effects. An unstructured covariance matrix will be employed to model the covariance of within subject effect and the Kenward-Roger approximation will be used to estimate the denominator degrees of freedom; if MMRM fails to converge then a covariance structure with fewer parameters from the following list will be employed according to the prespecified order in the list until the MMRM converges. The list of covariance structure will include Heterogeneous Toeplitz, Toeplitz, Heterogeneous Compound Symmetry, and Compound Symmetry. If a structured covariance is used, then the sandwich estimator will be used to estimate variance of the treatment effect estimator.

This primary analysis will include all observed post baseline data of the change from baseline in CDR-SB without imputation of missing values. The least squares (LS) means and difference in

LS means between elenbecostat treatment group and placebo, and corresponding 95% confidence interval (CI) will be presented.

Sensitivity/Supplementary Analyses

- 1). An MMRM analysis will be performed on the PPS.

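### The pooled amyloid PET test combines three tracers without a tracer term, which can cost some precision but does not bias the treatment contrast

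*SAP*

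**What the plan says.** SAP 5.4.2 (Key Secondary Endpoint Analysis) builds one response from three tracers: "The amyloid PET SUVR from three tracers (Florbetapir, Florbetaben, and Flutemetamol) will be standardized using the centiloid scale and combined for the key secondary endpoint". Each tracer has its own linear equation, with slopes of 205.72 (florbetapir), 175.57 (florbetaben) and 145.58 (flutemetamol) CL per SUVR unit. On the test itself: "The MMRM described for primary efficacy analysis will be used on the FAS to test the key secondary endpoints". Each endpoint brings its own baseline covariate, since the model is fitted "using baseline value corresponding to the response variable in the model".

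The model terms are in SAP 5.4.1: "with treatment group, visit, randomization stratification variables (ie, region [7 levels], clinical disease staging [MCI due to AD, early stage of mild AD", followed by AD medication use, ApoE4 status and treatment-by-visit, together with baseline and baseline-by-visit. The general covariate rule in SAP 5.3.2 says that efficacy models "will include the stratification variables (region, concurrent AD medication use, clinical disease staging", and adds ApoE4 status and baseline. Neither place names tracer. SAP 3.2 gives region, disease staging and AD medication use as the stratification factors.

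Tracer does appear elsewhere. SAP 5.3.4 lists it as a subgroup, "amyloid PET tracer (Florbetapir, Florbetaben, and Flutemetamol; only for amyloid PET SUVR", but "no significance tests will be performed in the subgroups", and the plot leaves PET out: "Forest plot for primary and key secondary endpoint (only ADCOMS) will be generated". SAP 5.4.2 also analyses other composite SUVR parameters separately by tracer. The only sensitivity analysis it names for a key secondary endpoint is for ADCOMS.

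**The concern.** Centiloid conversion puts the tracers on one scale. It does not guarantee that mean change over 24 months, or the noise around it, is the same for each tracer. A remaining difference in mean change would be a known, recorded source of variation that the model leaves in the residual. Because tracer was not stratified, nothing forces the arms to balance on it.

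What is at stake is precision in the only biomarker test left in the hierarchy. SAP 5.1.2 and 5.3.3 say the PET sample fell short of the plan, far enough that the individual-study PET tests were removed.

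**Working it through.** **1. Reproduce the plan's own conversion figures (SAP 5.4.2).**
- Florbetapir 1.2: 205.72 × 1.2 − 209.63 = 37.234 CL. Florbetapir 1.6: 205.72 × 1.6 − 209.63 = 119.522 CL.
- Back to florbetaben: (37.234 + 173.21)/175.57 = 1.198633; (119.522 + 173.21)/175.57 = 1.667324.
- Back to flutemetamol: (37.234 + 139.29)/145.58 = 1.212557; (119.522 + 139.29)/145.58 = 1.777799.

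All agree with the stated equivalents, so the equations are applied consistently. If a subject stays on one tracer (assumption), the intercept cancels in the change score. Only differences in tracer-specific change or noise remain.

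**2. Cost of omitting a tracer mean term.** The SAP gives no PET SD, tracer mix or tracer-specific change, so these are assumptions:
- mean changes of 0, g/2 and g CL for the three tracers, with g = 2, 5 or 10;
- residual SD s of 10 or 15 CL;
- mixes of equal thirds, 60/25/15 and 80/10/10.

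Between-tracer variance is v = Σpm² − (Σpm)². The SE ratio without versus with the term is √(1 + v/s²).
- Equal thirds, g = 5, s = 10: v = (0 + 6.25 + 25)/3 − 2.5² = 4.17; √1.0417 gives +2.1%.
- Equal thirds, g = 10, s = 10: v = 16.67; √1.1667 gives +8.0%.
- 80/10/10, g = 2, s = 15: v = 0.5 − 0.3² = 0.41; √1.0018 gives +0.1%.

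| Gap g between extreme tracers | SE increase over all mixes and SDs |
|---|---|
| 2 CL | 0.1-0.3% |
| 5 CL | 0.6-2.1% |
| 10 CL | 2.3-8.0% |

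**3. Type I error and power.** A simulation of a single-time-point linear model used 4000 runs per setting, mix 60/25/15, an assumed effect of 8 CL, and unequal residual SDs by tracer (14.4, 12.3 and 10.2 CL, from an assumed SUVR SD of 0.07).

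| Total N, gap | Type I without / with tracer | Power without / with tracer |
|---|---|---|
| 100, 5 CL | 5.3% / 5.1% | 83.2% / 83.2% |
| 100, 10 CL | 4.5% / 4.6% | 82.6% / 84.2% |
| 300, 10 CL | 5.1% / 5.0% | 99.9% / 99.9% |

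The Monte Carlo SE at 5% is √(0.05 × 0.95/4000) = 0.34 percentage points, so every type I figure is compatible with 5%.

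**4. Unequal noise.** If SUVR error is equal across tracers (assumption), the centiloid variance ratio of florbetapir to flutemetamol is (205.72/145.58)² = 2.0. With equal shares, one common covariance then costs about 8% in variance, or 4% in SE, against tracer-weighted analysis. If error instead scales with each tracer's range, the ratio is 1.0 and the cost is nil: the stated 82.288 CL span covers 0.400, 0.469 and 0.565 SUVR for florbetapir, florbetaben and flutemetamol. The SAP does not say which applies, and a tracer mean term would not recover this cost.

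**The case against.** The strongest reply is that nothing here is wrong or contradictory. Omitting a prognostic covariate from a randomised comparison leaves the estimate unbiased, the SAP harmonises the tracers with explicit equations, and step 3 shows almost no effect on error rates. That stands.

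A reader might infer that chance tracer imbalance adds a separate error to the estimate. A 10-point imbalance between tracers 5 to 10 CL apart would move the difference by 0.10 × 5 = 0.5 to 0.10 × 10 = 1.0 CL. That movement is already part of the sampling error that the SE measures. With SD 15 and an assumed 50 per arm, the SE is 15 × √(2/50) = 3 CL, so the shift is one-sixth to one-third of one SE. Counting it alongside the variance increase counts one thing twice.

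A reader might also infer that the SAP contradicts itself by making tracer a subgroup but not a covariate. It does not: age, sex, race and ethnicity are treated the same way.

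The by-tracer analyses will show tracer-specific results. For florbetapir and flutemetamol they include the same composite and reference region as the key secondary measure. That helps interpretation but leaves the pooled test unchanged. Region is in the model and would absorb part of any tracer difference if tracer use follows geography (assumption).

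Finally, the PET test is reached only if CDR-SB and ADCOMS both succeed, and the DSMB recommended termination on an unfavourable balance of risk and benefit. This limits the practical weight of the point.

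**Conclusion.** The point holds as a modest, avoidable loss of precision. The pooled model has no tracer term, and the untested subgroup and by-tracer summaries do not alter that. Any tracer difference in centiloid change that remains after calibration goes into residual variance. The SE cost is about 0.1-2.1% for gaps of 2 to 5 CL and 2.3-8.0% at 10 CL, conditional on the assumed SD of 10-15 CL and the assumed mixes. If no difference remains, the cost is zero.

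The documents do not support reading this as bias, type I inflation or an established twofold noise difference between tracers. The last depends wholly on assuming equal SUVR error.

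**What to change.** In SAP 5.4.2, add baseline tracer (three levels) and tracer-by-visit as fixed effects to the pooled centiloid MMRM, and report tracer counts by arm. Tracer is already recorded, since the conversion needs it. The cost is 2 degrees of freedom per visit.

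Do not add tracer-specific residual covariance to the confirmatory model. It would triple the covariance parameters in a small sample, make the final model depend on convergence, and fall outside the fallback order fixed in SAP 5.4.1.

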3.2 OVERALL STUDY DESIGN AND PLAN

This study is a 24 month treatment, multicenter, double-blind, placebo-controlled, parallel group Core Study with an open-label Extension Phase in EAD including mild cognitive impairment (MCI) due to AD and the early stages of mild AD. In addition, the MCI due to AD population will also be consistent with the research criterion for “Prodromal AD” in that episodic memory will be impaired on a list-learning task (International Shopping List Task [ISLT]). The Extension Phase is available for subjects who complete the Core Study, including the 3-month follow-up, and provides subjects with open-label treatment with elenbecestat for 24 months, or until commercial availability of elenbecestat or a lack of positive benefit-risk is determined, whichever comes first.

Study E2609-G000-301 and Study E2609-G000-302 will be combined, with a total of approximately 1900 randomized subjects; at least 850 subjects will be randomized in each study.

In this Core Study, subjects will be randomized, in a double blind manner, to receive either placebo or elenbecestat 50 mg per day (in 1:1 randomization ratio) for 24 months. Randomization will be stratified according to region (7 levels), clinical disease staging with no more than approximately 25% of the randomized subjects diagnosed with the early stages of mild dementia due to AD, and concurrent AD medication use. The 7 levels of the region are:

1. North America
2. Western Europe (including Oceania region and South Africa)
3. Eastern Europe
4. Japan
5. China
6. Other Asian countries
7. South America

The study is designed to have more frequent visits focused on safety assessments during the first 3 months of treatment.

Three longitudinal biomarker substudies will evaluate the effects of study treatment on the underlying pathophysiology of AD using amyloid PET, tau PET and/or CSF biomarkers. Participation in the substudies is optional and will require specific consent that will not affect

enrollment or treatment in the main study. The tau PET substudy will be offered to study-eligible subjects from select geographical sites (based on proximity to the tau PET ligand manufacturing sites) in the US who have an amyloid positive study-specific PET scan and who have also consented to participate in the amyloid PET substudy. Tau PET scanning will be performed using a sponsor-supplied tau PET imaging agent, eg, PI-2620.

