5.2 STUDY SUBJECTS

5.2.1 Definitions of Analysis Sets

The definitions of the analysis data sets are:

- The Randomized Set is the group of subjects who are randomized to study drug.
- The Safety Analysis Set is the group of subjects who receive at least 1 dose of study drug and have at least 1 postdose safety assessment. Safety Analysis Set will be used in the statistical analyses for safety. In the event that a subject received study drug different from the one to which this subject was randomized, the subject's safety data will be analyzed "as treated."
- The Full Analysis Set (FAS) is the group of randomized subjects who receive at least 1 dose of study drug and have baseline and at least 1 postdose primary efficacy measurement.
- The Per Protocol Analysis Set (PPS) is the subset of subjects in the FAS who sufficiently comply with the protocol. PPS will be used to conduct a sensitivity analysis of the primary efficacy endpoint. The criteria for exclusion from PPS are listed below:
 - MMSE <24 or CDR global score \neq 0.5 or CDR Memory Box score < 0.5 at screening
 - Condition that may contribute to cognitive impairment at screening
 - vascular dementia, lewy body dementia, PD, multiple sclerosis, epilepsy in medical history
 - Hachinski Score >4
 - Brain MRI exclusions
 - BMW [Section 4](#) Other MRI Abnormalities exclusions including:
 - Superficial siderosis
 - Lacunar infarct (2 or more)
 - Stroke involving a major vascular territory
(Defined by safety MRI data)
 - ISLT total recall and delayed recall impairment < 1 SD from age-adjusted norms at screening
 - Negative for amyloid pathology for all assessments performed at screening, ie PET and/or CSF.
 - Subject <50 or >85 years of age at consent
 - Subject was receiving AChEIs or memantine or both for AD but had not been on a stable dose for at least 12 weeks prior to baseline
 - At screening
 - Thyroid stimulating hormone (TSH) > upper limit of normal (ULN)

- Vitamin B12 < lower limit of normal (LLN) and methylmalonic acid MMA >0.41µm/L (if MMA available)
 - Illiteracy in medical history
 - Study drug compliance
 - < 67% up to planned last dose
- The PK Analysis Set is the group of subjects with at least 1 quantifiable elenbecestat plasma concentration with a documented dosing history.
- The PD Analysis Set is the group of subjects who have sufficient PD data to derive at least 1 PD parameter. The separate analysis set will be prepared for amyloid PET, tau PET, plasma, CSF, and vMRI assessments.

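### The two Cox analyses include no usable baseline severity score, and SAP sections 5.3.2 and 5.4.2 disagree on whether ApoE4 status is a covariate

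*SAP*

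**What the plan says.** SAP v2.0, section 5.4.2, specifies time to worsening of CDR scores on the FAS "using a Cox regression model for treatment effect, adjusting for randomization stratification factors". The conversion paragraph uses the same model: "This endpoint will be analyzed on the FAS using a Cox regression model for treatment effect, adjusting for randomization stratification factors". Neither paragraph names another covariate. Conversion is restricted by definition: "Time to conversion to dementia for subjects who were not clinically staged as dementia at baseline".

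Section 5.3.2 sets a general rule: "The primary, secondary, and exploratory efficacy endpoints will include the stratification variables (region, concurrent AD medication use, clinical disease staging", followed by ApoE4 status "and baseline value of the endpoint (if applicable) as covariates". It also says that the classification used at randomization supplies the covariate values.

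The one stratum that reflects severity is staging. Section 3.2 describes it as "clinical disease staging with no more than approximately 25% of the randomized subjects diagnosed with the early stages of mild dementia due to AD". Under section 5.2.1, FAS subjects must "have baseline and at least 1 postdose primary efficacy measurement", and the primary measure is CDR-SB.

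Section 5.3.3 leaves both endpoints outside the testing hierarchy. The SAP gives no hazard ratio, event count or power for either.

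**The concern.** Two things looked wrong.

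- **The covariate list is not settled.** Section 5.3.2 puts ApoE4 status into every secondary efficacy model; 5.4.2 leaves it out of both Cox models. A programmer cannot tell which list governs.
- **No baseline severity score enters under either list.** The plan itself treats baseline CDR-SB as informative. It is a covariate in the primary MMRM and in the ANCOVA after multiple imputation (5.4.1), it is tabulated in four bands from 0–1.5 to 6 or more (5.2.4), and it helps define the very mild subgroup (5.3.4).

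Leaving a prognostic covariate out of a Cox model moves the treatment hazard ratio toward 1, lowers power, and leaves chance imbalance in severity inside the estimate. Both studies stopped early, which shortens follow-up, so efficiency matters more than under the full design.

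**Working it through.** **1. The plan's own figure.** The only powered figure is for the primary endpoint (section 4). The difference is 0.25 × 1.46 = 0.365 and the SD is 2.05. Then n = 2 × (1.960 + 1.282)² × 2.05² / 0.365² ≈ 663 evaluable per arm; 663 / 0.70 gives 948 per arm, 1896 in total, against 1900 stated. It reproduces, but says nothing about the Cox endpoints.

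**2. Severity terms available to each Cox model.**

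| Term | Time to CDR worsening | Time to conversion |
|---|---|---|
| Staging (stratum) | Two levels, dementia capped near 25% | Essentially constant: subset is not staged as dementia |
| Region, AD medication (strata) | In; not severity scores | In; not severity scores |
| ApoE4 status | In under 5.3.2, absent in 5.4.2; not a severity score | Same |
| Endpoint's own baseline, if applicable | Global CDR, nearly all 0.5 | None exists |

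For global CDR, 5.2.1 makes any screening value other than 0.5 a per-protocol exclusion, and both worked examples in 5.4.2 start at 0.5. Staging is only essentially constant in the conversion subset because the randomization classification may differ from the actual one for a few subjects.

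**3. Simulation.** Hazard = λ·exp(g·x + log(HR)·treatment), where x is baseline CDR-SB in SD units. All of the following are assumptions except the 1:1 allocation, the 30% dropout, the 24-month limit and the planned N:

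- HR 0.75 given x; g = 0.3, 0.6 or 0.9; λ set so that 20%, 30% or 50% of placebo subjects have the event by 24 months.
- Worsening: N = 1900, with a 25% staging indicator (latent correlation 0.5 with x) in both models; 800 replicates.
- Conversion: N = 1424 (75% of 1900, made even), with no staging term; 1000 replicates.

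Each data set was fitted without and with x.

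| Placebo events | g | Worsening: HR | Power, % | Conversion: HR | Power, % |
|---|---|---|---|---|---|
| 20% | 0.3 | 0.753 → 0.751 | 63.7 → 66.0 | 0.749 → 0.748 | 54.7 → 55.4 |
| 20% | 0.6 | 0.756 → 0.748 | 64.0 → 69.1 | 0.751 → 0.744 | 54.9 → 57.9 |
| 20% | 0.9 | 0.765 → 0.748 | 62.4 → 69.8 | 0.765 → 0.747 | 50.6 → 55.9 |
| 30% | 0.3 | 0.755 → 0.753 | 84.8 → 86.4 | 0.755 → 0.752 | 71.7 → 73.3 |
| 30% | 0.6 | 0.760 → 0.749 | 79.5 → 85.1 | 0.762 → 0.749 | 66.9 → 74.5 |
| 30% | 0.9 | 0.770 → 0.746 | 75.6 → 85.0 | 0.772 → 0.746 | 64.8 → 75.3 |
| 50% | 0.3 | 0.752 → 0.748 | 97.5 → 98.0 | 0.755 → 0.750 | 90.4 → 91.6 |
| 50% | 0.6 | 0.771 → 0.753 | 95.5 → 97.5 | 0.764 → 0.746 | 88.6 → 93.8 |
| 50% | 0.9 | 0.786 → 0.750 | 90.6 → 97.1 | 0.788 → 0.749 | 81.4 → 93.8 |

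The gain is 0.5 to 9.4 points for worsening and 0.7 to 12.4 for conversion. With g = 0.3 it is at most 2.3 points; in the 20% worsening case the mean z statistic moves only from −2.365 to −2.379.

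**4. Type I error.** With HR = 1, g = 0.9 and 50% events (worsening set-up), rejection is 5.4% without x and 5.5% with it.

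**5. Cross-check.** Schoenfeld's formula, power = Φ(½·√d·|log HR| − 1.96), with d = 325 events gives Φ(9.01 × 0.288 − 1.96) = 0.74, close to the adjusted conversion models at 30% events (73.3% and 74.5%).

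**6. Shorter follow-up.** A separate simulation used staggered follow-up of 3 to 24 months, HR 0.80, 11% to 23% with events, and staging and AD medication in the model (700 replicates). Power went from 34.9 to 36.3, 58.6 to 61.3, 40.3 to 42.0 and 59.1 to 65.1%. In the strongest case the mean HR moved from 0.810 to 0.798.

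**Limits.** The Monte Carlo standard error of one power estimate near 50% is √(0.25/800) ≈ 1.8 points; in the main simulation (step 3), paired fitting makes the differences more precise. No comparator model held region or ApoE4, and only the one in step 6 held AD medication. The power levels in step 3 assume full planned follow-up and do not describe the terminated studies.

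**The case against.** The strongest reply is that nothing here is an error. A strata-adjusted Cox model tests treatment validly, and the adjusted and less adjusted hazard ratios are different conditional quantities, so a value nearer 1 is not a biased estimate of one common target. The endpoints are other secondary endpoints with no power claim. The gain rests on prognostic strength and event rates that the SAP does not give. All of this stands, and it keeps the point at the level of an efficiency improvement.

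Three further objections stand in part.

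- Section 8.5 defines CDR-SB as a sum of six domains but gives no scoring rule for global CDR. How much closer to a global 1 a high-scoring subject starts is therefore an inference.
- The plan does not adjust for baseline everywhere; the CDR-SB slope model in 5.4.2 lists no baseline score or stratum. Consistency alone does not settle the matter.
- The DSMB's September 2019 form reports no evidence of potential efficacy, so power to show benefit has less decision value. The tests are two-sided, however, and the same gain in precision would serve an effect in the harmful direction (reasoned, not simulated).

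A reader might infer that the Cox models adjust for nothing beyond the strata, and that their hazard ratios are therefore diluted and power lost as a matter of fact. The documents do not support that: 5.3.2 calls for ApoE4 status, and the size of any loss cannot be derived from the SAP.

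**Conclusion.** The point holds as a covariate list to reconcile and a low-cost gain in efficiency. Sections 5.3.2 and 5.4.2 conflict on ApoE4 for both Cox models, and under either reading neither model has a usable baseline severity score. The case is stronger for conversion, where the one severity-related stratum drops out.

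Adding baseline CDR-SB would be expected to raise power by about 0.5 to 9 points for worsening and 1 to 12 points for conversion. That range assumes a conditional hazard ratio of 0.75, 20% to 50% of placebo subjects with events by 24 months, and a log hazard ratio of 0.3 to 0.9 per SD of CDR-SB. At the weak end the gain is negligible. The strata-adjusted analysis remains valid, and type I error was essentially the same with and without the covariate in the setting tested. None of the objections shows a drawback to adjusting for a score that is already collected and already used in the primary model.

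**What to change.** In section 5.4.2, for both Cox models and for their sensitivity analyses that censor after intercurrent events, state one list: *adjusted for the randomization stratification factors, ApoE4 status and baseline CDR-SB (continuous)*. Align 5.3.2 by saying that, for these two endpoints, baseline CDR-SB takes the place of the endpoint's own baseline value.

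The cost is a change of SAP wording and added terms in the program. No subject is lost for want of a baseline CDR-SB, because FAS membership already requires it. The change should be made before unblinding; after that, the adjusted model should be reported as a labelled supplementary analysis.
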